1.0 General Information

***Enter the full title of your study:**

Improving Delivery of Patient-Centered Cardiac Rehabilitation

***Enter the study number or study alias**

Improving Delivery of Patient-Centered Cardiac Rehabilitation

* This field allows you to enter an abbreviated version of the Study Title to quickly identify this study.

2.0 Add Department(s)

2.1 List departments and/or research programs associated with this study:

Primary Dept?	Department Name
	UCSF - 138331 - M_MED-VAMC-ADMIN

5.0 Initial Screening Questions - Updated 9/13

(Note: You must answer every question on this page to proceed).

If you are converting to the new form, check questions 5.4, 5.6, 5.7, 5.8 and 5.10 before saving and continuing to the next section.

5.1 * Application type:

- Full Committee
- Expedited
- Exempt

5.2 * Risk level (Help Text updated 9/13):

- Minimal risk
- Greater than minimal risk

5.3 * Subject contact:

- Yes (including phone, email or web contact)
- No (limited to medical records review, biological specimen analysis, and/or data analysis)

5.4 * Funding (past or present):

- Funded or will be funded (external sponsor, gift, program or specific internal or departmental funds)
- Unfunded (no specific funds earmarked for this project)
- Unfunded student project

5.5 * The Principal Investigator and/or one or more of the key study personnel has financial interests related to this study:

- Yes
- No

If **Yes**, the Conflict of Interest Advisory Committee (COIAC) office may contact you for additional information.

5.6 * This is an investigator-initiated study:

- Yes
- No

5.7 * This study ONLY involves retrospective records review and/or identifiable biospecimen analysis:

- Yes
- No

5.8 * This is a clinical trial:

- Yes
- No

Clinical Trial Registration

"NCT" number for this trial:

NCT02105246

5.9 * This is a multicenter study:

- Yes
- No

5.10 * This application involves the study of unapproved or approved drugs, devices, biologics or in vitro

diagnostics:

Yes No

5.11 * This application involves a Humanitarian Use Device:

No
 Yes, and it includes a research component
 Yes, and it involves clinical care ONLY

5.12 * This study involves human stem cells (including iPS cells and adult stem cells), gametes or embryos:

No
 Yes, and requires CHR and GESCR review
 Yes, and requires GESCR review, but NOT CHR review

5.13 * This is a CIRB study (e.g. the NCI CIRB will be the IRB of record):

Yes No

5.14 * This application includes a request to rely on another IRB (other than NCI CIRB):

Yes No

Note: If this request is approved, the CHR will **NOT** review and approve this study. Another institution will be the IRB of record.

6.0 Funding

6.1 Identify all sponsors and provide the funding details. If funding comes from a Subcontract, please list only the Prime Sponsor: **Note: we require only a P Number OR an A Number for funding coming through UCSF. Please avoid these common errors in funding documentation:**

- **DO NOT add the A Number if a P Number was already provided OR update the A Number field when a new funding cycle begins. The IRB does NOT use this information or want these changes made.**
- **DO NOT add a grant continuation as a new funding source.**

External Sponsor:

View Details	Sponsor Name	Sponsor Type	Awardee Institution	Contract Type:	UCSF RAS "P number" or eProposal number	UCSF RAS System Award Number ("A" + 6 digits)
	Patient-Centered Outcomes Research Inst	05	UCSF		P0058380	

Sponsor Name:	Patient-Centered Outcomes Research Inst
Sponsor Type:	05
Sponsor Role:	Funding
Grant/Contract Number:	
Awardee Institution:	UCSF
Is Institution the Primary Grant Holder:	Yes
Contract Type:	
UCSF RAS "P number" or eProposal number:	P0058380
UCSF RAS System Award Number ("A" + 6 digits):	
Grant Number for Studies Not Funded thru UCSF:	
Grant Title:	
PI Name: (If PI is not the same as identified on the study.)	
Significant Discrepancy:	

Gift, Program, or Internal Funding (check all that apply):

- Funded by gift (specify source below)
- Funded by UCSF or UC-wide program (specify source below)
- Specific departmental funding (specify source below, if applicable)

List the gift, program, or departmental funding source:

6.2 If you tried to add a sponsor in the question above and it was not in the list, follow these steps:

- If funding has already been awarded or the contract is being processed by the Office of Sponsored Research (OSR) or Industry Contracts Division (ICD), your sponsor is already in the system and the project has an eProposal Proposal or Award number. Check with your department's OSR Staff or ICD Officer to ask how the sponsor is listed in the UC sponsor list and what the Proposal or Award number is. Click here to find your OSR staff and here to find your ICD staff.
- If your sponsor is not yet in the list, enter it in the box below.

Sponsor not in list

Only if your sponsor is not yet in the list, type the sponsor's name:

If the funding is administered by the UCSF Office of Sponsored Research, your study will not receive CHR approval until the sponsor and funding details have been added to your application.

6.3 * This study is currently supported in whole or in part by Federal funding OR has received ANY Federal funding in the past (Help Text updated 9/13):

Yes No

If **yes**, indicate which portion of your grant you will be attaching:

- The Research Plan, including the Human Subjects Section of your NIH grant or subcontract
- For other federal proposals (contracts or grants), the section of the proposal describing human subjects work
- The section of your progress report if it provides the most current information about your human subjects work
- The grant is not attached. The study is funded by an award that does not describe specific plans for human subjects, such as career development awards (K awards), cooperative agreements, program projects, and training grants (T32 awards) OR UCSF (or the affiliate institution) is not the prime recipient of the award

8.0 Studies Involving Other Sites

8.1 UCSF is the coordinating center:

Yes No

If **Yes**, describe the plan for communicating safety updates, interim results, and other information that may impact risks to the subject or others among sites:

Important information, including safety updates and interim results, will be communicated to other sites by means of study memoranda (SM). Study memoranda will be numbered sequentially in the order in which they are issued and a complete list will be stored at the coordinating center. Each of these documents will be prepared by coordinating center personnel, signed by the coordinating center's principal investigator, and then sent by email to the principal investigator and main study contact at each study satellite site.

If **Yes**, describe the plan for sharing modification(s) to the protocol or consent document(s) among sites:

All modifications to protocol and consent documentation will be communicated through the distribution of study memoranda to principal investigators and main study contacts at each study site. These documents will detail the exact changes made to protocol and consent documents, including specific change to language in the protocol and/or consent.

8.2 Check any other UC campuses with which you are collaborating on this research study:

- UC Berkeley
- UC Davis
- Lawrence Berkeley National Laboratory (LBNL)
- UC Irvine
- UC Los Angeles
- UC Merced
- UC Riverside
- UC San Diego
- UC Santa Barbara
- UC Santa Cruz

8.3 Are the above UC campuses requesting to rely on UCSF's IRB (check all that apply):

- Yes (Submit a reliance request through the UC IRB Reliance Registry)
- No (Complete IRB Approval Certification section)

10.0 Study Design

10.1 * Study design (Help Text updated 9/13):

Cardiac rehabilitation involves exercise training, education, and lifestyle counseling for patients with cardiac conditions. Home and center-based cardiac rehabilitation programs, if followed by patients, are equally effective in their benefits on risk factors, health-related quality of life, death, and clinical events following acute myocardial infarction or coronary revascularization. This study will compare the effectiveness of existing cardiac rehabilitation programs. The San Francisco VA Medical center offers a home-based (but not a center-based) cardiac rehabilitation program to patients who are hospitalized for myocardial infarction, percutaneous coronary intervention, or coronary artery bypass grafting. The other study sites offer a center-based (but not a home-based) cardiac rehabilitation to the same group of patients. All facilities have initiated a comprehensive CR intervention with 7 components:

1. Educate and engage stakeholders (grand rounds, posters, brochures, one-on-one meetings)
1. Automate referrals
1. Standardize templates and stop codes for consults, progress notes, exercise prescription, and the patients' Individualized Treatment Plans
1. Use database to track all patients referred; monitor % enrolled, number of sessions completed.
1. Standardize outcome assessment
1. For CABG patients, provide in-hospital assessment and phase I cardiac rehabilitation; coordinate care with home PT
1. Offer a phase II cardiac rehabilitation program within 6 months of hospitalization.

The only difference between the sites is that San Francisco offers a home-based cardiac rehab program and other sites will offer a center-based cardiac rehab program.

Research outcomes will include processes of care (% of eligible patients referred, % enrolled, average number of sessions completed, provider knowledge) and patient outcomes (6 minute walk distance, physical activity, quality of life, patient and caregiver satisfaction, re-hospitalization, mortality). The study will evaluate the effectiveness of each CR program on these outcomes. All 6 minute walk tests associated with the home-based portion of the study will be conducted at the San Francisco VA Medical Center.

In addition, research participants will be asked to participate in a total of 2 additional study visits. The visits will take place 3 months and 6 months after their enrollment in the cardiac rehabilitation program. Medical records will be reviewed and death certificates will be obtained for up to 10 years of follow-up. This protocol will require national access to VA electronic health records through CAPRI and/or VistAWeb.

10.2 If this is a clinical trial, check the applicable phase(s) (Help Text updated 9/13):

- Phase I
- Phase II
- Phase III
- Phase IV

11.0 Scientific Considerations

11.1 Hypothesis (Help Text updated 9/13):

This study has a hypothesis:

Yes No

If yes, state the hypothesis or hypotheses:

Patients undergoing home based cardiac rehabilitation will not differ in 6 minute walk time, physical activity, quality of life, patient and caregiver satisfaction, and re-hospitalization as compared with patients undergoing center-based cardiac rehabilitation.

11.2 * List the specific aims:

Aim 1. Determine whether automatic referral to home- vs. center-based CR increases patient participation in CR after hospitalization for myocardial infarction or coronary revascularization.

Aim 2. Among patients who choose to participate in CR, compare the effectiveness of home- vs. center-based CR on six-minute walk distance, quality of life, and healthcare expenditures.

Aim 3: Determine whether the effects of home vs. center-based CR differ by age, gender, race, ethnicity, distance from medical center, employment, socioeconomic status, social support, caregiver status, comorbid conditions, or patient preference.

11.3 Statistical analysis:

The outcomes listed will be measured at baseline, and then at 3 and 6 months following first visit to CR. Prior to inferential statistics, we will use descriptive statistics and graphs to explore distributions, univariate outliers, and basic bivariate associations with home- vs. center-based CR. We will then compare baseline characteristics of the two groups to examine differences on key subgroup variables including age and type of procedure resulting in the need for CR. Imbalanced baseline measures will be included as covariates in outcome analyses.

To appropriately model these nested data, we will use linear mixed models also called multilevel or hierarchical linear models. Our primary outcomes on which only the patient or their caregiver provide data will be analyzed using a multivariate regression model with a simple random -effects structure with repeated-measures. We anticipate that patients who agree to enroll in home-based CR will be different than those who agree to enroll in center- based CR. Therefore, we will use other variables measured at baseline to construct a propensity score for home- vs. center-based CR, and we will adjust the multivariable analyses for this propensity score. Planned subgroup analyses will include the effects of the following predictors on outcomes: age, gender, race/ethnicity, SES, distance to nearest facility that can provide rehabilitation, and presence of caregivers. We will determine whether these same socio-demographic factors are associated with patient preference. We will also conduct subgroup analyses where we have identical measures from patients and caregivers.

11.4 If this study has undergone scientific or scholarly review, please indicate which entity performed the review:

- Cancer Center Protocol Review Committee (PRC) (Full approval is required prior to final CHR approval for cancer-related protocols.)
- CTSI Clinical Research Center (CRC) advisory committee
- Departmental scientific review
- Other:

Specify **Other**:

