Test the hypothesis that patients undergoing home based cardiac rehabilitation will not differ in 6 minute walk time, physical activity, quality of life, patient and caregiver satisfaction, and re-hospitalization as compared with patients undergoing center-based cardiac rehabilitation.

Aim 1. Determine whether automatic referral to home- vs. center-based CR increases patient participation in CR after hospitalization for myocardial infarction or coronary revascularization.

Aim 2. Among patients who choose to participate in CR, compare the effectiveness of home- vs. center-based CR on six-minute walk distance, quality of life, and healthcare expenditures.

Aim 3: Determine whether the effects of home vs. center-based CR differ by age, gender, race, ethnicity, distance from medical center, employment, socioeconomic status, social support, caregiver status, comorbid conditions, or patient preference.

Study Design

Cardiac rehabilitation involves exercise training, education, and lifestyle counseling for patients with cardiac conditions. Home and center-based cardiac rehabilitation programs, if followed by patients, are equally effective in their benefits on risk factors, health-related quality of life, death, and clinical events following acute myocardial infarction or coronary revascularization. This study will compare the effectiveness of existing cardiac rehabilitation programs. The San Francisco VA Medical center offers a home-based (but not a center based) cardiac rehabilitation program to patients who are hospitalized for myocardial infarction, percutaneous coronary intervention, or coronary artery bypass grafting. The other study sites offer a center-based (but not a home-based) cardiac rehabilitation to the same group of patients. All facilities have initiated a comprehensive CR intervention with 7 components:

1. Educate and engage stakeholders (grand rounds, posters, brochures, one-on-one meetings)
2. Automate referrals

3. Standardize templates and stop codes for consults, progress notes, exercise prescription, and the patients' Individualized Treatment Plans
4. Use database to track all patients referred; monitor % enrolled, number of sessions completed.
5. Standardize outcome assessment
6. For CABG patients, provide in-hospital assessment and phase I cardiac rehabilitation; coordinate care with home PT
7. Offer a phase II cardiac rehabilitation program within 6 months of hospitalization.

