13.0 Sample Size and Eligibility

13.1 Number of subjects that will be enrolled at UCSF and affiliated institutions:

200

13.2 Total number of subjects that will be enrolled at all sites (Help Text updated 9/13):

400

13.3 Estimated number of people that you will need to consent and screen here (but not necessarily enroll) to get the needed subjects:

400

13.4 Explain how and why the number of subjects was chosen (Help Text updated 9/13):

Sample size estimation for the difference between two groups over four assessments assuming a linear trend. The estimate is based on a two-sided alpha of .05, power of .90, a constant correlation of 0.5 among all repeated measurements, and a 5% overall attrition. San Francisco will enroll 200 participants while the other centers will enroll 100 participants each with a study total of 400 participants. With these assumptions, a composite effect of .5 can be detected

13.5 * Eligible age range(s):

- 0-6 years
- 7-12 years
- 13-17 years
- 18+ years

13.6 Inclusion criteria:

- CABG within 6 months prior to first session
- PCI within 6 months prior to first session
- Acute MI within 6 months prior to first session

13.7 Exclusion criteria:

- Age < 18 years
- Pregnant
- Behavioral or cognitive limitations that interfere with performing exercise training
- Significant movement disorder that interferes with exercise training
- Blind, deaf or mute
- Homeless (or unstable housing anticipated during the next 3 months)
- LVEF <35% without ICD
- Staged PCI with significant remaining lesion
- Decompensated heart failure
- QTc > 500 msec and no ICD
- 6MWT < 75 m (post-op) or < 150 m (non-surgical)
- Long-term (>30 days) SNF placement
- Atrial arrhythmia not rate controlled
- Mobitz Type II or 3rd degree AV block without pacemaker
- Deceased
- History of unprovoked or exercise-induced VT, VF or syncope with no ICD
- Concerning ventricular ectopy in past 24 hours with no ICD (Lown grading system)
 - Polymorphic/multiform PVCs
 - Couplets, Salvos, or non-sustained VT
 - R on T pattern
 - >10 PVCs per minute

13.8 There are inclusion or exclusion criteria based on gender, race or ethnicity:

Yes No

If **yes**, please explain the nature and rationale for the restrictions:

14.0 Other Approvals and Registrations**14.1 * Do any study activities take place on patient care units:**

Yes No

If **Yes**, attach a letter of support for the study from the involved patient care manager(s).

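### The stated hypothesis is that home and center CR do not differ, but the planned difference test can only reject it: no margin or confidence-interval rule lets the study support it

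*Combined protocol and SAP*

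**What the plan says.** **Hypothesis.** The Objectives open with "Test the hypothesis that patients undergoing home based cardiac rehabilitation will not differ in 6 minute walk time", followed by physical activity, quality of life, patient and caregiver satisfaction, and re-hospitalization. Section 11.1 of the study application repeats it: "Patients undergoing home based cardiac rehabilitation will not differ in 6 minute walk time, physical activity, quality of life" and so on. No other hypothesis is stated.

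**Aims.** These are worded as comparisons. Aim 2, for example, is to "compare the effectiveness of home- vs. center-based CR on six-minute walk distance, quality of life, and healthcare expenditures".

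**Sample size (13.4).** "Sample size estimation for the difference between two groups over four assessments assuming a linear trend", with two-sided alpha .05, power .90, constant correlation 0.5 and 5% attrition. On allocation it says "San Francisco will enroll 200 participants while the other centers will enroll 100 participants each with a study total of 400 participants". On the size of effect, with no outcome or unit attached, it says "With these assumptions, a composite effect of .5 can be detected".

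**Analysis (11.3 and the matching Statistical Analysis Plan).** "we will use linear mixed models also called multilevel or hierarchical linear models", with covariate and propensity-score adjustment. The text refers to "Our primary outcomes on which only the patient or their caregiver provide data" without saying which outcomes these are. It gives no equivalence or non-inferiority margin, no confidence-interval rule and no criterion for concluding that the programs are alike.

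**Foreseen conclusion (17.4 and 17.5).** Section 17.4 describes the benefit to society if home CR is shown to be equitable to center CR. Section 17.5 justifies the risks partly by finding out whether home CR works as well as center CR.

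**The concern.** A two-sided test of a difference has two outcomes. A significant result rejects the no-difference hypothesis. A non-significant result leaves it standing without supporting it, because the same result arises when the programs are alike and when they differ by an amount the study cannot resolve. To support sameness, the plan would need to say how large a difference still counts as none, and to require the confidence interval to exclude anything worse. It says neither.

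At stake is the conclusion that sections 17.4 and 17.5 have in view. If the result is non-significant, the plan offers nothing else to rest that conclusion on. A real shortfall of home CR could then be reported as agreeing with the hypothesis, and a margin chosen after the results are seen would carry little weight.

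**Working it through.** **Inputs from 13.4:** 200 home and 200 center patients; 5% attrition, so 200 x 0.95 = 190 per arm; correlation 0.5; two-sided alpha .05; power .90; linear trend.

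**Assumptions added here, not in the plan:** independent patients; one continuous outcome in SD units; contrast equal to the home-minus-center difference in baseline-to-last-visit change under a linear trend. The linear trend appears only in the sample-size text; the analysis sections do not say that time enters the model linearly.

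**Per-patient variance of the fitted change** = (1 - 0.5) x L^2 / sum of (t - mean t)^2, where L is the length of follow-up:
- four equally spaced assessments: 0.5 x 9 / 5 = 0.900
- months 0, 3, 6, 12 (Statistical Analysis Plan): 0.5 x 144 / 78.75 = 0.914
- months 0, 3, 6 (11.3): 0.5 x 36 / 18 = 1.000

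**The plan's own figure first.** If .5 is in these SD units (assumption), n per arm = (1.960 + 1.282)^2 x 2 x variance / 0.5^2 = 75.7, 76.9 and 84.1. Dividing by 0.95 and rounding up gives 80, 81 and 89 per arm, or 160, 162 and 178 in total. The stated 400 is not reproduced. It may contain an allowance that 13.4 does not state, or .5 may be in another unit. That is a separate matter and errs towards a larger study.

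**Precision.** SE = sqrt(2 x variance / 190); 95% CI half-width = 1.96 x SE.

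**Chance that a true home deficit d is non-significant** = 1 - [Phi(d/SE - 1.96) + Phi(-d/SE - 1.96)]. The values of d are assumptions; the plan names no smallest important difference.

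| | 4 equally spaced | 0, 3, 6, 12 mo | 0, 3, 6 mo |
|---|---|---|---|
| SE (SD) | 0.097 | 0.098 | 0.103 |
| 95% CI half-width (SD) | 0.191 | 0.192 | 0.201 |
| d = 0.20 | 46% | 47% | 50% |
| d = 0.25 | 27% | 28% | 32% |
| d = 0.30 | 13% | 14% | 17% |
| d = 0.40 | 1.6% | 1.7% | 2.6% |
| d = 0.50 | 0.07% | 0.09% | 0.18% |

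**Sensitivity to the model.** A baseline-adjusted comparison at a single visit (assumption) has per-patient variance 1 - 0.5^2 = 0.75, so SE = sqrt(2 x 0.75 / 190) = 0.089. A deficit of 0.20 SD is then non-significant about 39% of the time.

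**Limits.** The rates are for one continuous outcome, not for all listed outcomes jointly, and do not apply to re-hospitalization. Between-site variance, or precision lost to propensity adjustment, would raise them.

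**The case against.** The best defense is that stating no difference is ordinary null-hypothesis wording, that 13.4 plans a two-sided test of exactly that, and that all three Aims can be answered by estimates with confidence intervals. The part about the Aims stands: Aim 1 even asks whether participation increases. The defense does not rescue the hypothesis. Read as a null, it can be rejected but never supported, whereas 17.4 and 17.5 foresee a conclusion of sameness.

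Four stronger readings are tempting, and the documents do not support them:
- **That the investigators will take a non-significant p-value as equivalence.** No section says so. The plan simply provides no alternative.
- **That any deficit below the .5 in 13.4 could pass unnoticed.** On the figures above, 0.40 SD is missed only 1.6-2.6% of the time.
- **That sizing for a difference is itself a fault, or that 400 is too few.** With a true difference of zero, a non-inferiority test at one-sided 0.025 needs the same number of patients as a two-sided 0.05 test for a difference equal to the margin. The decision rule is what is missing.
- **That there must be a single primary outcome.** Several outcomes, each with its own margin, would also be coherent.

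It is also fair to say that the percentages depend on a model the plan does not specify. They show the order of the risk and are not operating characteristics of the plan.

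**Conclusion.** The point holds. As written, the study can refute its stated hypothesis but has no means of supporting it, and so no prespecified basis for the sameness conclusion in 17.4 and 17.5. This follows from the text and needs no calculation. The size of the risk does rest on the assumptions listed: roughly two in five to one in two for a 0.20 SD deficit across the models tried, and small above about 0.3 SD. The data remain usable and the Aims are unaffected. The fault lies in the hypothesis and the missing rule for reading the result, and should be fixed before outcomes are analyzed.

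**What to change.** Keep N unchanged. In the Objectives, 11.1, 11.3 and the matching Statistical Analysis Plan text:

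1. Restate the hypothesis as estimating the home-minus-center difference.
2. Report the 95% CI of that difference for each outcome, from the models already planned.
3. State that a non-significant test will not be read as showing no difference, or that home CR is equitable to or as effective as center CR.

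If the sponsor wants to claim that home CR is as effective, it must also prespecify the outcome(s), the visit and a justified margin. For outcomes where higher is better, non-inferiority is claimed only if the lower limit of the two-sided 95% CI for home minus center lies above minus the margin. Otherwise the result is reported as inconclusive. Because all home patients come from San Francisco, any such claim must also say that program and site cannot be separated.

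**Cost.** Steps 1 to 3 are wording plus intervals that the planned models already yield. The optional claim adds the work of justifying a margin. Neither adds patients or visits. The downside is that a non-significant result alone no longer counts as support, and the study may end inconclusive on this question.

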The outcomes listed will be measured at baseline, and then at 3, 6, and 12 months following first visit to CR. Prior to inferential statistics, we will use descriptive statistics and graphs to explore distributions, univariate outliers, and basic bivariate associations with home- vs. center-based CR. We will then compare baseline characteristics of the two groups to examine differences on key subgroup variables including age and type of procedure resulting in the need for CR. Imbalanced baseline measures will be included as covariates in outcome analyses. To appropriately model these nested data, we will use linear mixed models also called multilevel or hierarchical linear models. Our primary outcomes on which only the patient or their caregiver provide data will be analyzed using a multivariate regression model with a simple random -effects structure with repeated-measures. We anticipate that patients who agree to enroll in home-based CR will be different than those who agree to enroll in center- based CR. Therefore, we will use other variables measured at baseline to construct a propensity score for home- vs. center-based CR, and we will adjust the multivariable analyses for this propensity score. Planned subgroup analyses will include the effects of the following predictors on outcomes: age, gender, race/ethnicity, SES, distance to nearest facility that can provide rehabilitation, and presence of caregivers. We will determine whether these same socio-demographic factors are associated with patient preference. We will also conduct subgroup analyses where we have identical measures from patients and caregivers.

Study Application (Version 1.14)

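### If the simple random-effects structure means a patient random intercept, the standard error of change from baseline will be too small at the last visit whenever correlation fades with time; an unstructured covariance avoids this at almost no cost.

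*Combined protocol and SAP*

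**What the plan says.** The Statistical Analysis Plan at the front of the document and section 11.3 of the study application use the same modeling text. For nested data, "we will use linear mixed models also called multilevel or hierarchical linear models". The primary outcomes with data from only the patient or the caregiver get a "simple random -effects structure with repeated-measures". Neither place names a random intercept, a random slope, a residual covariance, robust standard errors, the coding of time or the contrast to be tested.

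The only statement about correlation over time is in section 13.4, where the sample size assumes "a constant correlation of 0.5 among all repeated measurements".

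The number of visits is not settled:

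- Section 11.3: "The outcomes listed will be measured at baseline, and then at 3 and 6 months following first visit to CR". Section 10.1 likewise has follow-up at 3 and 6 months only.
- Front Statistical Analysis Plan: "The outcomes listed will be measured at baseline, and then at 3, 6, and 12 months following first visit to CR". The front Study Design section agrees with it.
- Section 13.4 sizes the study for "the difference between two groups over four assessments assuming a linear trend".

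**The concern.** The most natural reading of a simple random-effects structure is one random intercept per patient with independent residuals. That model has the same variance at every visit and the same correlation for every pair of visits, and nothing in the documents supports either as a fact about these patients. Section 13.6 admits patients up to 6 months after surgery, PCI or infarction, so baseline falls at different stages of recovery. Measurements further apart may also be less alike than adjacent ones.

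If the assumption fails, the estimated difference in change from baseline is still reasonable, but its model-based standard error is not. The study's hypothesis is that the two programs do not differ, so the confidence interval carries the conclusion. An interval that is too narrow overstates how closely the programs have been shown to match, and it also raises the false-positive rate of the test.

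**Working it through.** **The plan's own figure.** Section 13.4 gives 400 patients (200 home, 200 center), an effect of 0.5, "two-sided alpha of .05, power of .90", correlation 0.5, four assessments with a linear trend, and "a 5% overall attrition". For a difference growing linearly from 0 to 0.5 SD over four equally spaced visits:

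n per arm = 2(1.960 + 1.282)² × (1 − 0.5) × Σc² / (Σcd)², with c = −1.5, −0.5, 0.5, 1.5 and d = 0, 0.167, 0.333, 0.5. So Σc² = 5, Σcd = 0.833 and n = 75.7. Dividing by 0.95 gives 80 per arm, or 160 in total.

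This does not reproduce 400, and neither do the other readings tried (about 112 to 180 in total). Under these inputs 400 is more than enough. The point below does not depend on it.

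**Inputs.** Analyzed per arm: 200 × 0.95 = 190, about 380 in all. Equal variances, SD 1. The true correlations are assumptions: exponential decay with a 3-month correlation from 0.5 to 0.9, plus two other patterns.

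**Formula.** With balanced data, a random-intercept model estimates the within-patient variance as σ²(1 − mean ρ), averaging over all pairs of visits. The true variance of the between-group difference in change from baseline to visit k is (2/n) × 2σ²(1 − ρ₀ₖ). Hence

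model SE / true SE = √[(1 − mean ρ) / (1 − ρ₀ₖ)], and type I error = 2[1 − Φ(1.96 × ratio)].

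**Visits at 0, 3 and 6 months.** At a 3-month correlation of 0.7 the pairs are 0.7, 0.7 and 0.49, with mean 0.63.

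- 3 months: √(0.37/0.30) = 1.111
- 6 months: √(0.37/0.51) = 0.852, type I error 9.5%

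**Visits at 0, 3, 6 and 12 months.** At the same decay the six pairs are 0.7, 0.49, 0.240, 0.7, 0.343 and 0.49, with mean 0.494.

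- 3 months: √(0.506/0.30) = 1.299
- 6 months: √(0.506/0.51) = 0.996
- 12 months: √(0.506/0.76) = 0.816

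Ratios of model SE to true SE across the assumed decay:

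| Schedule | 3-month correlation | 3 months | 6 months | 12 months |
|---|---|---|---|---|
| 0/3/6 | 0.5 | 1.080 | 0.882 | – |
| 0/3/6 | 0.7 | 1.111 | 0.852 | – |
| 0/3/6 | 0.9 | 1.140 | 0.827 | – |
| 0/3/6/12 | 0.5 | 1.199 | 0.979 | 0.876 |
| 0/3/6/12 | 0.7 | 1.299 | 0.996 | 0.816 |
| 0/3/6/12 | 0.9 | 1.411 | 1.024 | 0.761 |

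The type I error runs from 8.4% to 10.5% at 6 months on the first schedule, and from 8.6% to 13.6% at 12 months on the second.

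**Other patterns** (0–3, 3–6, 0–6 months), three visits:

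- 0.50/0.80/0.40, where baseline is the odd visit out: mean 0.567. Ratios √(0.433/0.5) = 0.931 and √(0.433/0.6) = 0.850, so both are too small (type I error 6.8% and 9.6%).
- 0.50/0.50/0.50: both ratios are 1.000, so there is no error.

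**Simulation check.** Correlations 0.60/0.60/0.30, 190 per arm, 120 runs. The mean model SE was 0.1026 at both visits, against an empirical SD of 0.0951 at 3 months and 0.1163 at 6 months (closed form 0.0918 and 0.1214). With baseline as a covariate the direction was the same: 0.0915 against 0.0866 and 0.1022. The runs are few, so the closed form is the main evidence.

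**Difference in level at a visit.** With equal variances and separate means for each program and visit, the model SE is about 0.102 and the true value is √(2/190) = 0.1026. This contrast is not distorted.

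**The case against.** The strongest reply is that the plan never says random intercept. The sentence concerns outcomes with one source of data, and the same section separately mentions measures taken identically from patients and caregivers. There, *simple* could mean only that no patient-caregiver level is needed. The mention of repeated measures leaves room for a residual covariance, and robust standard errors are not excluded. This stands: a reader might infer that the plan forces equal correlation, but the text does not go that far. The constant 0.5 in section 13.4 makes the reading likely without fixing the analysis model. If something else is meant, the covariance is simply unstated and the same sentence of the plan still needs replacing.

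A reader might also infer that the 6-month interval is bound to be too narrow and the 3-month interval too wide. The documents do not support that as a general statement. It needs the 0/3/6 schedule, a change-from-baseline contrast and correlation that depends only on the time gap. On the four-visit schedule the narrow interval moves to 12 months. If baseline is atypical, as the recovery argument suggests, both intervals can be too narrow.

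Finally, the contrast is not named, and section 13.4 plans on a linear trend. With a single slope there is no separate 3-month result. However, on the 0/3/6 schedule the slope equals (6-month value − baseline)/6, so its standard error carries the same shortfall as the 6-month change.

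**Conclusion.** The point holds conditionally, as a cheap improvement. It rests on three assumptions: a random intercept with independent residuals, model-based standard errors, and a contrast in change from baseline or adjusted for it. Under these, correlation that fades with time makes the standard error at the last visit too small: by 12% to 17% at 6 months on the three-visit schedule, or 12% to 24% at 12 months on the four-visit schedule. The size depends on a decay that the documents do not give, and it is zero if correlation is constant.

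It does not follow that the sample size is inadequate or that every comparison is affected. At 0.60/0.60/0.30 the true 6-month SE of 0.1214 gives a detectable effect of 3.242 × 0.1214 = 0.39 SD at 90% power, still below the 0.5 in section 13.4 if that figure is in SD units.

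**What to change.** In the front Statistical Analysis Plan and in section 11.3, replace the simple random-effects structure with visit as a category, program-by-visit terms and an unstructured within-patient covariance. Name the contrast to be tested; if the linear trend of section 13.4 is intended, take it as a contrast of the visit means in this model. State the fallback if the model does not converge: a random intercept with robust standard errors.

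Reconcile the visit schedule across the front Study Design and Statistical Analysis Plan, sections 10.1 and 11.3, and the four assessments in section 13.4, because the visit at risk depends on it.

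The cost is a sentence or two. The covariance has 6 parameters for three visits or 10 for four, instead of 2, which is negligible with about 380 patients. The model stays valid if correlation is constant.
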